6.3.2 Open-label Treatment Period

After the 2 days of the Month 12 DBPCFC, at Visit 13, all subjects (Part A and Part B) were to continue treatment with Viaskin Milk in an open-label manner, at the highest

dose of Viaskin Milk selected for Part B (500 µg of cow's milk protein), based on safety data of Part A subjects. The Viaskin Milk open-label treatment period was to continue until Month 24 for all subjects and until Month 48 for the subjects who entered the study extension. If a subject experienced reactions after the DBPCFC at Visit 13 that warranted postponing the application of the first patch of the open-label treatment period, it was permitted, at the discretion of the Investigator, to delay the application of the first patch of the open-label treatment up to a maximum of 7 days after Visit 13.

To increase the safety of subjects at the beginning of the open-label treatment period, in particular for subjects crossing over from placebo to the active Viaskin Milk treatment, the daily duration of application was again to be adapted from Visit 13 for the first weeks of treatment as follows:

- 6 hours of daily application during the first week
- 12 hours of daily application during the second week
- 24 hours of daily application from the third week onwards

At the time of Protocol Amendment 5, all subjects were currently receiving active treatment with Viaskin Milk 500 µg. **The switch to Viaskin Milk 300 µg will not require a progressive increase of application duration, and all subjects will be able to start with 24 hours of daily application of Viaskin Milk 300 µg.**

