Subjects from both Part A and Part B were randomized to receive treatment with Viaskin Milk or placebo for 12 months (randomized double-blind treatment period), after which a second DBPCFC was performed. The primary analysis of this study was conducted after data have been collected up to Month 12 visits including both days of the DBPCFC at Month 12. Consequently, results from the safety and efficacy data collected in all Part A and Part B subjects up to and including the Month 12 visits were reported in the 12-Month Clinical Study Report (CSR).

This document is confidential

Statistical Analysis Plan

After the Month 12 DBPCFC, all subjects from Part A and Part B were to continue treatment with active Viaskin Milk 500 μ g, the highest dose determined to be safe, for up to a maximum of 36 months (DBPCFCs at Month 24, 36 and 48). Following results of the 12-month blinded period, all eligible subjects who wish to continue participation in the study switched from Viaskin Milk 500 μ g to Viaskin Milk 300 μ g for 24 additional months of treatment, as per protocol Amendment 5, independently of the duration of previous treatment (Optional DBPCFC at 12 and/or 24 months after switch to Viaskin Milk 300 μ g dose).

A final End-of-Study (EOS) visit will be performed for all subjects when they completed or stopped the study. The EOS visit was to take place 2 weeks after the last DBPCFC at Month 24 for the subjects completing the study at Month 24, or 2 weeks after the last DBPCFC at Month 48, for subjects completing the study extension at Month 48. For subjects switching to Viaskin Milk 300 μ g, the EOS visit will take place 2 weeks after the end of the 24-month treatment period at this dose.

Three-hundred-and-eight children and adolescent subjects have been screened, 198 were randomized in this study, 18 subjects in Part A and 180 subjects in Part B. In Part B, the randomization was stratified by site and by age group (children 2 to 11 years old at the time of Visit 1; adolescents 12 to 17 years old at the time of Visit 1).

The total duration of the study will be approximately 6 years and the total duration of participation in the study will differ for each individual subject and could be up to approximately 6 years.

[Figure 1](#) of the study protocol version 6.0 presents a summary of the enrolment process into Part A and Part B of the study, and [Figures 2](#) and [3](#) present the overview of the study design.

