3.4 TREATMENT ASSIGNMENT & BLINDING

3.4.1 Part A

In Part A, subjects were randomized in 3 successive cohorts of 6 subjects each to receive Viaskin Milk or placebo in a 2:1 ratio. The safety of the 3 doses of Viaskin Milk was assessed over a 3-week treatment period for each dose before proceeding to Part B.

The analysis of the cumulative safety data allowed the selection of the 3 Viaskin Milk doses (150µg, 300µg, and 500µg of cow's milk protein) for randomization into Part B of the study. The screening of subjects in Part B of the study continued when the enrolment

This document is confidential

Statistical Analysis Plan

in Part A was complete, however no subject was randomized into, or treated in, Part B before the review of the safety data from Part A has been completed by both the DSMB and the Food and Drug Administration. A pause in the randomization allowed for this safety review to occur and recommendations to be released.

All subjects in Part A continued their randomized blinded treatment at their assigned initial dose of treatment (150 μ g, 300 μ g or 500 μ g Viaskin Milk or placebo) up to Month 12.

After the Month 12 DBPCFC, all subjects in Part A shall continue treatment in an open-label manner for another 12 months with Viaskin Milk at the highest dose selected (500 μ g of cow's milk protein), based on the safety data of Part A.

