3.4.2 Part B

3.4.2.1 Method of Assigning Subjects to Treatment Groups

In Part B, 180 additional subjects were randomized (1:1:1:1 ratio) to receive Viaskin Milk 150 μ g, Viaskin Milk 300 μ g, Viaskin Milk 500 μ g or placebo up to Month 12.

All subjects were assigned an identification number at Visit 1. The IWRS randomized all eligible subjects and assigned the appropriate treatment kit. IWRS managed the inventory and assignment of treatment to subjects at the kit level. The site pharmacists dispensed the drug product according to the IWRS recommendations. Subjects at each dose level were randomly assigned to receive either Viaskin Milk or placebo according to a computer-generated randomization code that was produced by an unblinded study statistician at the Contract Research Organization (CRO) in accordance with the Standard Operating Procedures (SOPs) of the CRO. In addition, the randomization to treatment for subjects randomized in Part B were stratified by site and by age group (children 2 to 11 years old at the time of Visit 1; adolescents 12 to 17 years old at the time of Visit 1).

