9.3.3.3 Subject-Year Analysis

A subject-year analysis was performed on the same parameter as described for the overview tables above on the whole treatment period overall and for each age-group for the SS. The subject year analysis should be presented according to treatments received (not randomized). E.g., subject randomized as placebo and treated during one year with Placebo then treated with Viaskin Milk 500 μ g during 2 years should account for 1 patient-year in Placebo column and 2 patient-year in Viaskin Milk 500 μ g column.

This document is confidential

Statistical Analysis Plan

Additionally, a subject-year analysis presented the total number of subject-years, the number of subjects with a TEAE (respectively a TEAE considered related to IP) per subject-year and the number of TEAEs (respectively TEAEs considered related to IP) per subject-year, for each dose level and by SOC and PT on the whole treatment period overall and for each age-group for the SS.

Separate listings were performed additionally:

- SAEs
- TESAEs
- Adverse events of specific interest (AESI):
 - o Local AESIs.

These local TEAEs of interest will be identified following methodology described in [16.1 Appendix 1](#).

- o Systemic AESI considered related to IP.
- o Systemic AESI (whether related or not).

These systemic TEAEs of interest will be identified following methodology described in [16.2 Appendix 2](#).

- AEs leading to discontinuation
- TEAEs leading to epinephrine intake

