9.3.4.3 Subject-Year Analysis

Analysis by subject-year will be performed for the OLS-300 equivalently as described in [Section 9.3.3.3](#):

- a) The treatment durations and the respective AEs of subjects randomized to Placebo or Viaskin Milk 150 μ g in the DB-period will be assigned to the treatment arm "Placebo" or "Viaskin Milk 150 μ g", respectively.
- b) The treatment durations and the respective AEs of subjects randomized to Viaskin Milk 300 μ g in the DB-period and the whole OL-300 period will be added to the treatment arm "Viaskin Milk 300 μ g".

This document is confidential

Statistical Analysis Plan

- c) The treatment durations and the respective AEs of subjects randomized to Viaskin Milk 500µg in the DB-period and the whole OL-500 period will be added to the treatment arm "Viaskin Milk 500µg".

These treatment durations in days will be divided by 365.25 to get the subject-years. The number of AEs will be divided by the respective subject-years.

9.4 SYMPTOMS ELICITED DURING THE DBPCFC.

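### SAP 9.3.4.3 gives one adverse event rate per dose column, but the columns mix first-active-year and later time so differently that they are not comparable if rates or recording change with time on treatment

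*SAP*

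**What the plan says.** SAP 9.3.4.3 builds the OL-300 subject-year table on the OLS-300 in three items.

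- Time and AEs of subjects randomised to placebo or 150 µg "in the DB-period will be assigned to the treatment arm" of that name. No later time is added to these two columns.
- For 300 µg, time and AEs "in the DB-period and the whole OL-300 period will be added to the treatment arm".
- For 500 µg, time and AEs "in the DB-period and the whole OL-500 period will be added to the treatment arm".

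Each rate is the AE count divided by subject-years. SAP 9.3.3.3, which 9.3.4.3 follows, sets columns by treatment received rather than by randomised arm, so open-label time from every initial arm enters the 300 µg and 500 µg columns. Neither section splits or adjusts by time since first active patch.

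Protocol 6.3.2 records that everyone was on active 500 µg when the switch to 300 µg was introduced. It describes a stepwise start of wear time after Month 12, "in particular for subjects crossing over from placebo to the active Viaskin Milk treatment, the daily duration of application was again to be adapted", and no such step at the switch to 300 µg.

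**The concern.** The 150 µg column is made up entirely of subjects in their first year on an active patch. Most of the 300 µg column is time from subjects who already had active treatment behind them. The 500 µg column lies between, because it also holds the first active year of the former placebo subjects. If AEs become rarer with time on treatment, or are recorded less completely, dose is confounded with time on treatment.

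The documents give two reasons to take this seriously. The stepwise start shows that the first weeks of active treatment were handled with more caution. Prompted contact also thins out. After Day 1, a Part B subject has 8 visits and 7 calls in the first year (Protocol Table 2). After the switch visit there are 2 to 3 visits and 3 calls in the first OL-300 year, then 2 to 3 visits and 2 calls in the second, before the final follow-up (Protocol Tables 6 and 7).

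The OL-300 overview and incidence tables (SAP 9.3.4.1 and 9.3.4.2) are by initial treatment group. The subject-year table is the OL-300 AE output arranged by dose received, so a reader will naturally compare its columns.

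**Working it through.** The documents state no subject-year total and no AE rate, so the only plan figure to reproduce is the number randomised.

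**Arm sizes.** SAP 3.1: "198 were randomized in this study, 18 subjects in Part A and 180 subjects in Part B". SAP 3.4.1: "subjects were randomized in 3 successive cohorts of 6 subjects each to receive Viaskin Milk or placebo in a 2:1 ratio", which gives 4 subjects per dose and 6 on placebo. Part B is 180 at 1:1:1:1 (SAP 3.4.2.1), so 180/4 = 45 per arm. Each active arm has 45 + 4 = 49 and placebo 45 + 6 = 51. Check: 3 × 49 + 51 = 198, as stated.

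**Share of first-active-year time, f.** The base case lets every subject contribute full time. The table is restricted to subjects who switched, but if the same fraction of each arm switched, that fraction cancels from f. OL-300 time is 2 years at the final analysis and 1 year at the Year 1 analysis. Mean OL-500 time, d, is not given (the maximum is 3 years), so d = 1 to 3 is an assumption. So is that each former placebo subject spends the first active year in OL-500.

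| Column | First-active-year subject-years | All subject-years | f |
|---|---|---|---|
| 150 µg | 49 | 49 | 100% |
| 300 µg, final | 49 | 49 + 2 × 198 = 445 | 11.0% |
| 300 µg, Year 1 | 49 | 49 + 198 = 247 | 19.8% |
| 500 µg, d = 1 | 49 + 51 = 100 | 49 + 198 = 247 | 40% |
| 500 µg, d = 2 | 100 | 49 + 396 = 445 | 22% |
| 500 µg, d = 3 | 100 | 49 + 594 = 643 | 16% |

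If mean OL-300 time is 1.5 years, the 300 µg share is 49/(49 + 297) = 14.2%. Unequal retention (90% of the 300 µg arm against 60% of the others, or the reverse) gives 14% or 8%.

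**Effect at equal dose risk.** Let r be the later-year rate divided by the first-active-year rate. The documents do not give r. The expected 300/150 rate ratio is f + (1 − f) × r.

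- Final analysis (f = 0.110): r = 1 gives 1.00; r = 0.8 gives 0.110 + 0.890 × 0.8 = 0.82; r = 0.5 gives 0.56; r = 0.25 gives 0.33.
- Year 1 analysis (f = 0.198): r = 0.8 gives 0.84; r = 0.5 gives 0.60.
- An apparent halving at the final analysis needs r of (0.5 − 0.110)/0.890 = 0.44 or less.

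**A force in the other direction.** SAP 9.10.2 summarises itching, redness and swelling from diaries for the first 3 months and as AEs afterwards. Suppose, for illustration only, that 60% of AEs are local and go unrecorded as AEs for a quarter of the first year. The recorded first-year rate is then 1 − 0.25 × 0.6 = 0.85 of the true rate, and the ratio becomes (0.110 × 0.85 + 0.890 × r)/0.85. That is 1.16 at r = 1 and 0.63 at r = 0.5.

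**The case against.** The strongest reply is that unequal mixing does no harm unless rates change with time, and the documents give no rate by year. With flat rates the ratio is exactly 1.00. The stepwise start is a precaution, not evidence of rates, and it also shortens wear in the first two weeks. The absence of a step at the switch is explained by subjects already wearing a higher dose. The diary rule leaves even the direction open for local reactions. In addition, the OLS-300 leaves out early leavers and subjects with poor compliance (Protocol 4.4.2). If early leavers had more AEs, first-year rates in this table are already lowered. All of this stands, and it is why the point is conditional.

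A second reply is that like-for-like counts are already planned. Randomised-year AE tables by dose, and OL-500 tables by initial group, are in SAP 9.3.3.1 and 9.3.3.2; OL-300-only tables are in 9.3.4.1 and 9.3.4.2. This limits the harm but leaves the pooled rates as they are.

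A third reply is that the item for 300 µg could be read as covering only subjects randomised to 300 µg. The share would then be 49/147 = 33%, and the ratio 0.67 at r = 0.5. The treatment-received rule in 9.3.3.3 speaks against that reading, and 33% against 100% would still be unbalanced.

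Finally, Protocol 8.1.7.1 presents the subject-year analysis as descriptive information on longer-term safety, with no test or decision attached. That is correct.

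**Conclusion.** The dose columns in SAP 9.3.4.3 are not comparable if AE rates, or AE recording, change with time on treatment. First-active-year time is 100% of the 150 µg column, about 11% of the 300 µg column at the final analysis (about 20% at Year 1), and about 16% to 40% of the 500 µg column. These shares rest on proportional retention, full OL-300 time and the assumed range of OL-500 duration. The imbalance itself follows from the column definitions.

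A reader might infer that equally risky doses would be bound to show far fewer events per year on 300 µg. The documents do not support that. The ratio runs from 1.00 with flat rates through 0.82 to 0.56 as later rates fall to 0.8 and to half, and early under-recording could push it above 1. A reader might also infer that the table flattered 300 µg into being chosen. It could not have done so: that dose was selected from the completed 12-month results, with no safety concern reported at any dose (Protocol 6.2; SAP 3.4.2.2).

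Because the table is descriptive and randomised-year tables by dose exist, the change is worth making but its priority is modest.

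**What to change.** In SAP 9.3.4.3, present subject-year rates separately for the double-blind columns, OL-500 and OL-300. Alternatively, split each active column into the first 12 months since first active patch and later time. Keep former placebo subjects' first active year identifiable. State that between-dose safety comparisons use the double-blind columns only. Add that, within the OLS-300, those columns hold only subjects who later switched, so the Safety Set tables in 9.3.3 remain the randomised reference.

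With the split by time since first active patch, equally risky doses have an expected ratio of 1.00 within each year on active treatment, whatever r is. The first active year offers about 49 subject-years per dose from the double-blind period, before the OLS-300 restriction.

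The cost is a few more table columns, each with fewer subject-years and so less precise rates, from dates already held. No new data are needed. The 9.3.3.3 analysis is reported as done and kept for traceability (SAP section 2), so it needs at most a matching footnote.

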9.4.1 Double-blind Month 12 and OL-500 analyses

The symptoms elicited during the DBPCFC (as they are expressly provoked) are differentiated from TEAEs and TESAEs.

SAEs elicited during the DBPCFC were tabulated overall and for each age group, in total and by (initial actual) treatment group (placebo/dose level/overall active), by system organ class and preferred term for each time point of the DBPCFC in the SS, OL-500, respectively - discriminated between Milk- and Placebo-Formula.

SAEs elicited during any DBPCFC were tabulated overall and for each age group, in total and by (initial actual) treatment group (placebo/dose level/overall active), by system organ class and preferred term in the SS - discriminated between Milk- and Placebo-Formula.

Objective and subjective symptoms appearing during the DBPCFCs (which are not reported in the AE form unless they are SAEs) were summarized overall and for each age group, in total and by (initial actual) treatment group (placebo/dose level/overall active) by time point of the DBPCFC and severity in the SS, OL-500, respectively - discriminated between Milk- and Placebo-Formula.

9.4.2 OL-300 Analyses

SAEs elicited during the optional DBPCFC will be tabulated overall and for each age group, in total and by (initial actual) treatment group (placebo/dose level/overall active), by system organ class and preferred term for each time point of the DBPCFC in the analyzed OL-300 Period for the OLS-300. Incidences will be calculated with respect to the number of subjects participating on the respective DBPCFC and discriminated between Milk- and Placebo-Formula.

SAEs elicited during any DBPCFC will be tabulated overall and for each age group, in total and by (initial actual) treatment group (placebo/dose level/overall active), by system organ class and preferred term in the SS - discriminated between Milk- and Placebo-Formula.

Objective and subjective symptoms appearing during the DBPCFCs (which are not reported in the AE form unless they are SAEs) will be summarized overall and for each age group, in total and by (initial actual) treatment group (placebo/dose level/overall active) by time point of the DBPCFC and severity in the OL-300 Period - discriminated between Milk- and Placebo-Formula.

This document is confidential

Statistical Analysis Plan

9.5 VITAL SIGNS

9.5.1 General

Vital signs include heart rate (beats/minute), systolic blood pressure (mmHg), diastolic blood pressure (mmHg), and respiratory rate (breaths/minute).

Vital signs of potential clinical significance for children and adolescents are given in Table 4:

Table 4: Vital signs of potential clinical significance for children and adolescents

Vital Sign	Criteria for Clinically Significant Abnormalities
Heart rate	> 120 beats per minute or an increase from pre-dosing of > 20 beats per minute, or < 50 beats per minute or a decrease from pre-dosing of > 20 beats per minute
Systolic blood pressure	> 140 mmHg or an increase from pre-dosing of > 40 mmHg, or < 90 mmHg or a decrease from pre-dosing of > 30 mmHg
Diastolic blood pressure	> 90 mmHg or an increase from pre-dosing of > 30 mmHg, or < 50 mmHg or a decrease from pre-dosing of > 20 mmHg

The investigators are assessing, whether any of the abnormal values are clinically significant. Clinically significant abnormal values will be recorded as an AE.

9.5.2 Double-blind Month 12 and OL-500 analyses

Observed vital sign values and absolute changes from baseline were summarized using descriptive statistics overall and for each age group, visit and time point in total and by treatment group (placebo/dose level/overall active) on the SS for the randomized blinded treatment period (Months 0 to 12).

Same analysis was performed overall and for each age group, visit and time point in total and by initial actual treatment group on the OLS-500 for the Viaskin Milk 500 μ g open-label treatment period (Months 12 to switch to Viaskin Milk 300 μ g). Similarly, the last value in the Viaskin Milk 500 μ g open-label treatment period was summarized.

Values that are potentially clinically significant will be flagged in the vital signs listings.

9.5.3 OL-300 Analyses

The following vital signs values will be summarized using descriptive statistics overall and for each age group, visit and time point in total and by initial actual treatment group (placebo/dose level/overall active) on the OLS-300.

This document is confidential

Statistical Analysis Plan

- Absolute values at Month 0, Month 12, last value prior to switch to Viaskin Milk 300 μ g and all scheduled visits in the analyzed OL-300 period
- Changes from last value prior to any active treatment
- Changes from last value prior to switch to Viaskin Milk 300 μ g

Values that are potentially clinically significant will be flagged in the vital signs listings.

9.6 PHYSICAL EXAMINATION

9.6.1 General

Physical examination results are categorized in normal, abnormal, and not done.

9.6.2 Double-blind Month 12 and OL-500 analyses

Physical examination results, including complete observation of the skin were summarized overall and for each age group, visit and time point in total and by treatment group (placebo/dose level/overall active) on the SS for the randomized blinded treatment period.

Same analysis was performed overall and for each age group, visit and time point in total and by initial actual treatment group on the OLS-500, for the Viaskin Milk 500 μ g open-label treatment period. Similarly, the last value in the Viaskin Milk 500 μ g open-label treatment period was summarized.

Respective shift tables with respect to Month 0 were produced, if applicable.

9.6.3 OL-300 Analyses

Physical examination results, including complete observation of the skin will be summarized overall and for each age group, visit and time point in total and by initial actual treatment group (placebo/dose level/overall active) on the OLS-300 for the analyzed OL-300 period.

9.7 PATCH SITE SKIN EXAMINATION

9.7.1 General

Examination of the skin at the site of patch application is graded from Grade 0 (negative) up to Grade 4 (erythema, vesicles).

